8.3 Adverse Events and Serious Adverse Events

The definitions of an AE or SAE can be found in Section 10.2 (Appendix 2).

AE(s) will be reported by the patient (or, when appropriate, by a caregiver, surrogate, or the patient's legally authorized representative).

The investigator and any qualified designees are responsible for detecting, documenting, and recording events that meet the definition of an AE or SAE and remain responsible for following up AEs that are serious, considered related to the study drug or study procedures, or that caused the patient to discontinue the study (see Section 7).

8.3.1 Time Period and Frequency for Collecting Adverse Events and Serious Adverse Events Information

All AEs and SAEs will be collected from the time of the first study drug administration until Day 104. Medical occurrences that begin before the start of study drug but after obtaining informed consent will be recorded on the Medical History/Current Medical Conditions section of the CRF, not the AE section.

All SAEs will be recorded and reported to the sponsor or designee immediately and under no circumstance should this exceed 24 hours, as indicated in Section 10.2 (Appendix 2). The investigator will submit any updated SAE data to the sponsor within 24 hours of it being available.

The investigators are not obligated to actively seek AEs or SAEs after conclusion of the study participation. However, if the investigator learns of any SAE, including a death, at any time after a patient has been discharged from the study, and he/she considers the event to be reasonably related to the study drug or study participation, the investigator must promptly notify the sponsor.

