9.4.2 Part 1 Primary Endpoints

9.4.2.1 Safety and Tolerability

All AEs will be coded using the most recent version of MedDRA. The incidence of AEs will be summarized by SOC and PT. Similar summaries will be produced for AEs by severity, SAEs, treatment related AEs, and AEs leading to discontinuation. AEs are collected from the first dose of study drug, thus all AEs are considered treatment emergent AEs.

The ECG results will be presented by visit, summarizing the continuous measurements based on the average of triplicate values, including the QT, QTc, QRS, RR, PR intervals, as well as change from baseline values, and clinically significant changes in heart rate and rhythm.

Reported values and change from baseline values of hematology, clinical chemistry and urinalysis (and the determinations relevant to the normal ranges and appropriate clinically significant or CTCAE toxicity gradings) will be summarized by laboratory test for each assessment day, using appropriate descriptive statistics.

Vital signs (systolic and diastolic blood pressure, pulse rate, respiratory rate, and oral temperature) will be summarized by assessment day showing absolute values, change from baseline values, and clinically significant changes (including orthostasis) using appropriate descriptive statistics.

Physical and neurological examinations will be summarized by assessment day showing shift from baseline.

Protocol TB006AD2102

Protocol Date and Version: 15 Oct 2021; v 3.0

The C-SSRS assessments will be presented in a by-subject listing.

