10.2.1 Definition of AE

AE Definition

- An adverse event (AE) is any untoward medical occurrence in a patient or clinical study patient, temporally associated with the use of study drug, whether or not considered related to the study drug.
- NOTE: An AE can therefore be any unfavorable and unintended sign (including an abnormal laboratory finding), symptom, or disease (new or exacerbated) temporally associated with the use of study drug.

Events Meeting the AE Definition

- Any abnormal laboratory test results (hematology, clinical chemistry, or urinalysis) or
 other safety assessments (eg, ECG, radiological scans, vital signs measurements),
 including those that worsen from baseline, considered clinically significant in the
 medical and scientific judgment of the investigator (ie, not related to progression of
 underlying disease).
- Any new condition detected or diagnosed after study drug administration even though it may have been present before the start of the study.
- Signs, symptoms, or the clinical sequelae of a suspected drug-drug interaction.
- Signs, symptoms, or the clinical sequelae of a suspected overdose of either study drug
 or a concomitant medication. Overdose per se will not be reported as an AE/serious AE
 (SAE) unless it is an intentional overdose taken with possible suicidal/self-harming
 intent. Such overdoses should be reported regardless of sequela.

Events NOT Meeting the AE Definition

- Any clinically significant abnormal laboratory findings or other abnormal safety
 assessments that are associated with the underlying disease, unless judged by the
 investigator to be more severe than expected for the patient's condition.
- The disease/disorder being studied or expected progression, signs, or symptoms of the disease/disorder being studied, unless more severe than expected for the patient's condition.
- Medical or surgical procedure (eg, endoscopy, appendectomy): the condition that leads to the procedure is the AE.
- Situations in which an untoward medical occurrence did not occur (social and/or convenience admission to a hospital).

Protocol TB006AD2102

Protocol Date and Version: 15 Oct 2021; v 3.0

 Anticipated day-to-day fluctuations of pre-existing disease(s) or condition(s) present or detected at the start of the study that do not worsen.

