9.4.1. PARTIAL DATES

Although partial dates will not be 'filled up' in this study, some assumptions will be made in regards partial dates for background calculation/classification purposes as appropriate (for AEs, prior/concomitant medications etc.)

Table 1. Handling of Partial Dates

Parameter	Missing	Additional Conditions	Imputation
Start date	D	M and Y same as M and Y of first dose of study drug	Date of first dose of study drug
		M and/or Y not same as date of first dose of study drug	First day of month
	D and M	Y same as Y of first dose of study drug	Date of first dose of study drug
		Y prior to Y of first dose of study drug but same as Y of screening date	Date of screening date
	D, M and Y	None - date completely missing	Date of first dose of study drug
Stop date	D	M and Y same as M and Y of last dose of study drug	Date of last dose of study drug
		M and/or Y not same as date of last dose of study drug	Use last day of month
	D and M	Y same as Y of last dose of study drug	Date of last dose of study drug
		Y not same as Y of last dose of study drug	Dec 31
	D, M and Y	None - date completely missing	No imputation, but assume ongoing

D = day, M = month, Y = year
Note: In all cases, if an estimated start date is after a complete stop date, use the first day of the stop date month. Similarly, if the estimated stop date is before a complete or imputed start date, use the last day of the start day month.
In all cases, if it cannot be determined if the AE/medication occurred prior to or after the first dose of study drug infusion, the AE should be defined as treatment emergent, and medication will be considered as concomitant medication.

9.4.2. MISSING VALUE IMPUTATION FOR EFFICACY ENDPOINTS – PART 2

Apart from handling conventions and assumptions applicable to partial/missing data points mentioned above, there will be additional imputation for missing efficacy assessments listed under:

- CDRS – Sum of Boxes total score
- MMSE score
- NPI score

For these imputations, the missingness will be considered as missing at random (MAR). There will be no imputation for individual missing values, but missing data will be imputed implicitly using Mixed Model Repeated Measures (MMRM).

The MMRM analysis will be performed for above listed efficacy endpoints as described in Section 9.5.

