12.1. ADVERSE EVENTS

The following AE definitions are applicable to both protocol parts of this study:

- AE reporting period: Defined from start of first dose of study drug infusion on Day 1 up to and including End of Study.
- AE: Any untoward medical occurrence in a subject.
- Treatment-emergent AE (TEAE): Defined as any AE that started on or after first dose of study drug infusion within the studies' AE reporting period.
- SAE: Defined as any AE that is indicated as serious on the AEs Details eCRF, as per investigator's assessment.
- Related AE: Defined as any AE that is indicated as related to study drug on the AEs Details eCRF, as per investigator's assessment.
- AE leading to discontinuation: Defined as any AE that has an "other action taken" indicated as "withdrawn from study" on the AEs Details eCRF.

All AEs will be coded using the MedDRA version 22.1, Sep 2019. The following AE items will be listed separately for each protocol parts using the SAS:

- All AEs
- AEs leading to study discontinuation
- Serious AEs
- AEs leading to death (if applicable)

The following items are planned to be presented in summary tables showing event incidence and corresponding subject count, experiencing said AE/AE type using the SAS, by treatment groups using SAS:

- AE overview, including row items for frequency of subjects [n(%)] experiencing:
 - At least one AE
 - AEs by toxicity grade
 - Grade 1
 - Grade 2
 - Grade 3
 - Grade 4
 - Grade 5
 - Serious AEs

- Related AEs
- Non-related AEs
- AEs leading to study discontinuation
- AEs leading to death
- AEs by system organ class (SOC) and preferred term (PT)
- AEs by descending incidence of PT
- AEs by toxicity grade (Common Terminology Criteria for Adverse Events [CTCAE] grading)
- Related AEs by SOC and PT
- Related AEs by descending incidence of PT.
- Serious AEs
- AEs resulting in death
- AEs leading to study discontinuation

Only TEAEs will be used for summarization of all tables, but for listing all AEs will be counted. The TEAE status will be derived using the AE start and stop dates as per definition provided at the start of this section. For partial dates see [Section 9.4.1](#).

The data for these presentations will be obtained from the Adverse Events Details eCRF.

AE assignment to CTCAE toxicity grades is explained in [Table 2](#) below.

Table 2. CTCAE Grades

Grade	Grade Description	Grade Details

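### The SAP tabulates only AEs with a recorded start on or after first dose, so an AE first detected after dosing but entered with an earlier onset can drop out of the by-arm tables

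*Protocol*

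**What the plan says.** **Protocol.** Section 10.2.1 lists among events that qualify as AEs "Any new condition detected or diagnosed after study drug administration even though it may have been present before the start of the study". Its general note also admits a "symptom, or disease (new or exacerbated) temporally associated with the use of study drug". For analysis, section 9.4.2.1 applies no onset test: "AEs are collected from the first dose of study drug, thus all AEs are considered treatment emergent AEs". On collection, section 8.3.1 states: "Medical occurrences that begin before the start of study drug but after obtaining informed consent will be recorded on the Medical History", and keeps those occurrences off the AE section of the CRF.

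**SAP.** Section 12.1 defines a treatment-emergent AE by its start: "Defined as any AE that started on or after first dose of study drug infusion within the studies' AE reporting period". The classification is mechanical: "The TEAE status will be derived using the AE start and stop dates". Its scope is complete: "Only TEAEs will be used for summarization of all tables, but for listing all AEs will be counted". The tables listed there include serious AEs, AEs resulting in death and AEs leading to study discontinuation. Section 9.4.1 supplies partial-date rules and a fallback: if timing relative to first dose cannot be determined, "the AE should be defined as treatment emergent, and medication will be considered as concomitant medication". Section 8, which records departures from the protocol, names only the dose-proportionality assessment.

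**The concern.** The two documents define different sets of treatment-emergent AEs. Under the protocol the set is everything on the AE form. Under the SAP it is the subset with a start date on or after first dose, with no provision for an event that was first detected, or that worsened, after dosing. Moreover, the SAP's contrast between tables and listings presupposes non-emergent AEs, a class that protocol 9.4.2.1 says is empty.

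AE and SAE incidence is a primary endpoint in Part 1 and a secondary endpoint in Part 2. Patients are over 50 and may be on stable treatment for chronic conditions, so a previously unrecognized or worsening illness is a plausible form in which harm could appear. The listings would still show such a record, but they give no incidence by arm, and the comparison between TB006 and placebo is read from the tables.

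**Working it through.** The documents give no figure for this point, so there is none to reproduce. The check applies the SAP rule to the kinds of record an AE form could hold.

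**Inputs.** The TEAE definition and tabulation rule (SAP 12.1); start-date imputation (SAP 9.4.1, Table 1); the AE definition (protocol 10.2.1); the treatment-emergent rule (protocol 9.4.2.1). For illustration I assume a screening date of 20 January 2022 and a first dose on 10 February 2022.

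**Rule.** Tabulated if and only if the start date, recorded or imputed, is on or after first dose.

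| Record on the AE form | Start date used | In SAP tables? |
|---|---|---|
| Onset after first dose (1 March 2022) | as recorded | yes |
| First detected after dosing, complete onset before first dose (5 January 2022) | as recorded | **no** |
| First detected after dosing, day missing, earlier month (January 2022) | 1 January 2022 | **no** |
| Day missing, month of first dose (February 2022) | 10 February 2022 | yes |
| Day and month missing, year of first dose | 10 February 2022 | yes |
| Day and month missing, earlier year that is not the screening year (2020) | Table 1 gives no rule | not settled |
| Onset wholly missing | 10 February 2022 | yes |
| Exacerbation dated at the worsening (1 March 2022) | as recorded | yes |
| Exacerbation dated at original disease onset (1 June 2019) | as recorded | **no** |

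Under protocol 9.4.2.1 all nine are treatment-emergent. Under the SAP all nine are listed, but three are certainly not tabulated. The fallback in SAP 9.4.1 does not reach those three, because each date places the start before first dose.

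**What the filter does.** AE collection starts at first dose, and protocol 8.3.1 sends occurrences that begin between consent and first dose to medical history. Apart from recording errors, an AE-form record with a pre-dose start should therefore be one that protocol 10.2.1 admits: a condition first detected after dosing, or an exacerbation dated at original onset. So the filter either does nothing or removes protocol-defined AEs.

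**Are such dates plausible?** Protocol 10.2.3 asks for the date of onset and prefers a diagnosis to individual signs or symptoms. For a disease diagnosed on Day 40, an investigator could properly enter an earlier onset. Section 10.2.2 gives invasive or malignant cancers as examples of medically important serious events, so this class can include SAEs.

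**Scale.** The weight of one patient in an incidence row is 1 divided by the number in the group:

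- Part 1 active group: 1/6 = 16.7 percentage points
- Planned Part 2 arm: 1/58 = 1.7 percentage points

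A row changes only if that patient has no other qualifying event in it. These figures say what one patient is worth. They do not estimate how often it happens.

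**The case against.** The strongest reply is that the SAP test largely repeats the protocol's own collection rule. AEs are gathered only from first dose, and protocol 8.3.1 already directs earlier occurrences to medical history, so few AE-form records should carry a pre-dose start. This stands as a limit on frequency. It also shows that part of the conflict lies inside the protocol: a condition that began between consent and first dose but was found after dosing is medical history under 8.3.1 and an AE under 10.2.1. It does not remove the problem, because 10.2.1 expressly admits conditions present before the study.

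Second, an exacerbation is most naturally dated at its worsening. Protocol 10.2.1 excludes pre-existing conditions that do not worsen, which makes the worsening the event, and 10.2.3 has each change in AE severity recorded as an event. An exacerbation so dated is tabulated. This stands, and makes the exacerbation limb conditional on a site entering the original onset. Neither document states which date to enter. The SAP cites an eCRF specification that might settle it, but it is not among the documents available.

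Third, 10.2.1 says only that the condition may have been present, so its onset will often be unknown. A wholly missing start is imputed to first dose and tabulated. This also stands, and leaves the records with a determinable pre-dose date.

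A reader might infer something stronger: that all first-detected conditions and exacerbations, including serious or fatal ones, automatically disappear from the results. The documents do not support that. Exclusion depends on the date entered, and SAP 12.1 lists every AE, with separate listings for serious AEs, AEs leading to death and AEs leading to discontinuation.

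**Conclusion.** The point holds in a limited form. As written, SAP 12.1 gives the wrong result for a definable class of protocol AEs: records with a complete onset date before first dose, or a month-level date in a month before that of first dose. These would mainly be conditions first detected after dosing. SAP section 8 does not declare the departure.

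The number of records affected cannot be derived from the documents. It is zero if sites always enter the date of detection or worsening as the start.

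The conclusion rests on two assumptions. First, no unseen CRF instruction fixes the start date at detection or worsening. Second, protocol 9.4.2.1, which sits under Part 1, also governs Part 2. Section 9.4.5 refers Part 2 safety presentation to itself, evidently a cross-reference slip, but the same AE definition and collection period apply to both parts.

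**What to change.** Make one of two changes in SAP 12.1:

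- tabulate every record on the AE form, as protocol 9.4.2.1 implies; or
- define a TEAE as an AE that first occurs, is first detected, or worsens on or after first dose.

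Either covers the SAE, fatal-AE and discontinuation tables, so removing the filter from those tables separately is unnecessary. Declare any remaining difference from the protocol in SAP section 8. Reconcile protocol 8.3.1 with 10.2.1 for conditions that began before dosing but were found afterwards. A sentence in the CRF instructions on which onset date to enter would help.

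The cost is a wording change and one derivation flag, with no new data and no change to the design. The downside is that a few conditions of earlier onset will enter the tables. Because recording is blinded, this should affect both arms alike.

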10.2.2 Definition of Serious Adverse Event

If an event is not an AE per definition above, then it cannot be an SAE even if serious conditions are met (eg, hospitalization for signs/symptoms of the disease under study, death due to progression of disease).

An SAE is defined as any untoward medical occurrence that, at any dose, meets one or more of the criteria listed:

a. Results in death

b. Is life threatening

The term 'life threatening' in the definition of 'serious' refers to an event in which the patient was at risk of death at the time of the event. It does not refer to an event that hypothetically might have caused death if it were more severe.

c. Requires inpatient hospitalization or prolongation of existing hospitalization

In general, hospitalization signifies that the patient has been detained (usually involving at least an overnight stay) at the hospital or emergency ward for observation and/or treatment that would not have been appropriate in the physician's office or outpatient setting. Complications that occur during hospitalization are AEs. If a complication prolongs hospitalization or fulfills any other serious criteria, the event is serious. When in doubt as to whether "hospitalization" occurred or was necessary, the AE should be considered serious.

Hospitalization for elective treatment of a pre-existing condition that did not worsen from baseline is not considered an AE.

d. Results in persistent or significant disability/incapacity

- The term disability means a substantial disruption of a person's ability to conduct normal life functions.
- This definition is not intended to include experiences of relatively minor medical significance such as uncomplicated headache, nausea, vomiting, diarrhea, influenza, and accidental trauma (eg, sprained ankle) that may interfere with or prevent everyday life functions but do not constitute a substantial disruption.

e. Is a congenital anomaly/birth defect

f. Other medically important serious event:

Protocol TB006AD2102

Protocol Date and Version: 15 Oct 2021; v 3.0

Medical or scientific judgment should be exercised in deciding whether SAE reporting
is appropriate in other situations such as important medical events that may not be
immediately life threatening or result in death or hospitalization but may jeopardize the
patient or may require medical or surgical intervention to prevent one of the other
outcomes listed in the above definition. These events should usually be considered
serious.

Examples of such events include invasive or malignant cancers, intensive treatment in an emergency room or at home for allergic bronchospasm, blood dyscrasias or convulsions that do not result in hospitalization, or development of drug dependency or drug abuse.

10.2.3 Recording and Follow-Up of AE and/or SAE

AE and SAE Recording

- When an AE/SAE occurs, it is the responsibility of the investigator to review all
 documentation (eg, hospital progress notes, laboratory reports, and diagnostics reports)
 related to the event.
- The investigator will then record all relevant AE/SAE information in the case report form (CRF).
- It is **not** acceptable for the investigator to send photocopies of the patient's medical records in lieu of completion of the AE/SAE CRF page.
- There may be instances when copies of medical records for certain cases are requested. In this case, all patient identifiers, with the exception of the patient number, will be redacted on the copies of the medical records before submission.
- The investigator will attempt to establish a diagnosis of the event based on signs, symptoms, and/or other clinical information. Whenever possible, the diagnosis (not the individual signs/symptoms) will be documented as the AE/SAE.
- The investigator must assign the following AE attributes:
 - o AE diagnosis or syndrome(s), if known (if not known, signs or symptoms);
 - Dates of onset and resolution (if resolved);
 - Severity (or toxicity defined below);
 - Assessment of relatedness to study drug or other protocol-required therapies and
 - o Action taken. If AE severity changes, record each change as a single event.
- The following should be considered when recoding SAEs:
 - Death is an outcome of an event. The event that results in the death should be recorded and reported on both an SAE and CRF.
 - For hospitalizations, surgical, or diagnostic procedures, the illness leading to the surgical or diagnostic procedure should be recorded as the SAE, not the procedure itself.

Protocol TB006AD2102

Protocol Date and Version: 15 Oct 2021; v 3.0

Assessment of Severity

The investigator will make an assessment of severity for each AE and SAE reported during the study per the NCI CTCAE version 5.0 (see Section 10.2.5). Toxicities that are not specified in NCI CTCAE will be defined as follows:

- Grade 1: Mild; asymptomatic or mild symptoms; clinical or diagnostic observations only; intervention not indicated.
- Grade 2: Moderate; minimal, local or noninvasive intervention indicated; limiting
 age-appropriate instrumental ADL (eg, preparing meals, shopping for groceries or clothes,
 using the telephone, managing money).
- Grade 3: Severe or medically significant but not immediately life-threatening; hospitalization or prolongation of hospitalization indicated; disabling; limiting self-care ADL (eg, bathing, dressing and undressing, feeding self, using the toilet, taking medications).
 - An AE that is assessed as severe should not be confused with an SAE. Severe is a category utilized for rating the severity of an event; and both AEs and SAEs can be assessed as severe. An event is defined as 'serious' when it meets at least 1 of the predefined outcomes as described in the definition of an SAE, NOT when it is rated as severe.
- Grade 4: Life-threatening consequences; urgent intervention indicated.
- Grade 5: Death related to AE.

Assessment of Causality

- The investigator is obligated to assess the relationship between study drug and each occurrence of each AE/SAE.
- A "reasonable possibility" of a relationship conveys that there are facts, evidence, and/or
 arguments to suggest a causal relationship, rather than that a relationship cannot be ruled
 out.
- The investigator will use clinical judgment to determine the relationship.
- Alternative causes, such as underlying disease(s), concomitant therapy, and other risk
 factors, as well as the temporal relationship of the event to study drug administration, will
 be considered and investigated.
- The investigator will also consult the IB in his/her assessment.
- For each AE/SAE, the investigator must document in the medical notes that he/she has reviewed the AE/SAE and has provided an assessment of causality.
- There may be situations in which an SAE has occurred and the investigator has minimal
 information to include in the initial report. However, it is very important that the
 investigator always makes an assessment of causality for every event before the initial
 transmission of the SAE data.

Protocol TB006AD2102

Protocol Date and Version: 15 Oct 2021; v 3.0

 The investigator may change his/her opinion of causality in light of follow-up information and send an SAE follow-up report with the updated causality assessment.

- The causality assessment is one of the criteria used when determining regulatory reporting requirements.
- Causality assessments are defined below:
 - Causality assessments that indicate the event is "Not Drug Related":
 - Unrelated: The event is related to an etiology other than the study drug administration (the alternative etiology must be documented in the patient's medical record).
 - Unlikely: The event is unlikely to be related to the study drug and likely to be related to factors other than study drug.
 - Causality assessments that indicate the event is "Drug Related":
 - Possible: There is an association between the event and the administration of study drug and there is a plausible mechanism for the event to be related to the study drug; but there may also be alternative etiology, such as characteristics of the patient's clinical status or underlying disease.
 - Probable: There is an association between the event and the administration of study drug and there is a plausible mechanism for the event to be related to the study drug, and the event could not be reasonably explained by known characteristics of the patient's clinical status or an alternative etiology is not apparent.
 - Definite: There is an association between the event and the administration of study
 drug and there is a plausible mechanism for the event to be related to the study drug
 and causes other than the study drug have been ruled out and/or the event re-appeared
 on re-exposure to the study drug.

Follow-up of AEs and SAEs

- The investigator is obligated to perform or arrange for the conduct of supplemental
 measurements and/or evaluations as medically indicated or as requested to elucidate
 the nature and/or causality of the AE or SAE as fully as possible. This may include
 additional laboratory tests or investigations, histopathological examinations, or
 consultation with other health care professionals.
- If a patient dies during participation in the study or during a recognized follow-up period, the investigator will provide the sponsor with a copy of any post-mortem findings including histopathology.
- New or updated information will be recorded in the originally completed CRF.
- The investigator will submit any updated SAE data to the sponsor within 24 hours of receipt of the information.

Protocol TB006AD2102

Protocol Date and Version: 15 Oct 2021; v 3.0

